X-Ray - Dental Bitewing/Image	 (0.5 mrem)	0 mrem
X-Ray - Extremity (hand/foot)	 (0.1 mrem)	0 mrem
CT Scans - Head	 (200 mrem)	0 mrem
CT Scans - Chest	 (700 mrem)	0 mrem
CT Scans - Abdomen	 (800 mrem)	0 mrem
CT Scans - Pelvis	 (600 mrem)	0 mrem
CT Scans - Extremity	 (10 mrem)	10 mrem
CT Scans - Angiography (heart)	 (1200 mrem)	0 mrem
CT Scans - Angiography (head)	 (1000 mrem)	0 mrem
CT Scans - Spine	 (600 mrem)	0 mrem
CT Scans - Whole Body	 (1275 mrem)	0 mrem
CT Scans - Cardiac	 (300 mrem)	0 mrem

In vivo Three-Dimensional Determination of OA Brace Effectiveness

[name], PhD¹

¹University of Tennessee

Knoxville, TN

July 11, 2019

Send Correspondence To:

[name]
University of Tennessee
[name],
[name]
[contact]
[contact]
Email: [contact]

DATA ANALYSIS

Once the subjects have completed the activity, the fluoroscopic videos will be stored digitally and specific frames of interest will be captured from the video and exported into the preprocessing software.

Our 3D to 2D registration technique will be used to overlay the 3D models of the bones on their projection in the 2D fluoroscopic image. The fluoroscopic video would be digitized into frames and corrected for distortion. From here, the distortion-free images would be used with the 3D to 2D registration technique to extract *in vivo* patient femorotibial kinematics, which involves overlaying the 3D models of the components on their projection in the 2D fluoroscopic image.

Statistical analysis of the data will be carried out to analyze the two cohorts. All variables will be denoted as continuous. The data will be first checked for normality using the Shapiro-Wilk test. Only when the data is found to be normally distributed will parametric tests be used; otherwise, non-parametric tests will be used. The data will also be tested for equality of variance using the Barlett's test and Levene's test. The final selection criterion for the type of test to conduct will be based on the check for normality, as well as the check for equal variance. Therefore, for all the continuous variables, the following tests will be used:

1. Student's t-test (when the data is normally distributed and has equal variance).
2. Welch Anova test (when the data is normally distributed but has unequal variance).
3. Wilcoxon Mann Whitney U-test (when the data is not normally distributed).

All statistical tests will be carried out at 95% confidence level ($\alpha=0.05$) and will be performed using JMP® Statistical DiscoveryTM (SAS Institute Inc., Cary, NC) software.

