On the scheduled day of data collection, there will be at least two UT researchers present (which could also include the PI), as well as a study PI, (Drs. [name], [name]; [name], [name], [name], [name] [Sub-Investigators]) to conduct the fluoroscopic evaluation. Each subject will be asked to perform gait without the assistance of an offloading brace (Figure 1a). Then, each subject will be fitted with a Breg, off-the-shelf OA brace and will perform normal gait while under fluoroscopic surveillance (Figure 1b). To ensure each brace was fitted properly, Breg will be asked to send either a sales representative or an engineer to the evaluation site. Therefore, the sales representative or engineer will be asked to fit their brace on each of the subjects. This individual will sign a pledge of confidentiality.

[figure not shown]

Figure 1. Subject on a treadmill perform gait without a brace (a) and with a brace (b).

A Radiation Technician (RT) employed by Porter Adventist Hospital will perform the actual fluoroscopy procedure, following the subjects' OA knee with the unit as the activity is performed with and without the OA brace; only the knee joint (from the fluoroscopy machine) will be recorded on the fluoroscopy footage. The UT researchers, graduate research assistants (GRAs), which may include any of the following - [name], [name], [name], [name], [name] – will be present, although they will not perform the actual fluoroscopy procedure. They will be present during the fluoroscopy procedure to walk subjects through the activities, answer any questions that may arise, ensure data collection equipment is set up as needed and serve as consultants to the RT.

Any of these UT individuals, or study staff from Colorado Joint Replacement, will consent the participants. They will meet with each potential participant individually to make sure s/he has been properly informed of the procedures and to help with any of the IC form. CMR researchers will inform all subjects that they do not have to participate and are free to leave if they wish and will answer any questions subjects may have about the study. Participation is entirely voluntary.

Participants will be asked to practice the activity to ensure they can comfortably complete it and experience no pain with the fluoroscopy machine off (no radiation). The practice portion of the data collection without radiation will not be video-recorded.

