Study data will then be uploaded onto a secure server that University of Tennessee researchers will use to conduct the kinematic analysis using a model-fitting approach, the relative pose of knee implant components will be determined in 3D from a single-perspective fluoroscopic image by manipulating a CAD model in 3D space.

Using a model-fitting technique, the 3D bones will be overlaid onto the fluoroscopic images to determine amount of medial OA offloading. Successive fluoroscopic images of each subject's stance phase, with and without the OA brace, will be downloaded to a computer. Images will be captured at five instances during stance-phase of gait: heel strike, 33% of stance phase, mid-stance, 66% of stance-phase and at toe-off. A comparative analysis will be conducted for each subject while wearing the OA brace and with their non-braced test. Then, the amount of medial condylar separation will be assessed for each subject.

[figure not shown]

Figure 2. Example of 3D bone creation.

CT Scan

Participants will be asked to schedule a CT scan at Porter Adventist Hospital at their convenience within 1 month of the initial data collection day. To ensure subject safety, CT will be limited to the affected knee and the rest of patient's body will be protected from radiation with lead protection. The CT scan will be limited to the study knee and will image 6 inches distal on the tibia and 6 inches proximal on the femur.

Private Health Information/Medical Record Data

It is not anticipated that the subjects' medical files should need to be accessed for any PHI for the study for recruitment or for the conduct of the study itself. However, contact information from patient files will be acquired for inquiring as to whether or not patients would be willing to participate. The only subject-specific data that will be necessary will be measurements of medial condyle separation from the medial tibial plateau for each subject with and without a brace. Researchers will acquire the measurements with the brace while they are conducting the data collection. Researchers may also acquire the subjects' medial condyle separation without the brace while they are present for data collection. However, if this is not possible or time does not permit, Colorado Joint Replacement staff may send that information to UT researchers via secure transfer (e.g., UT Vault).

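### The SAP plans independent-group tests for braced versus unbraced gait, although every subject is measured in both conditions

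*SAP*

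**What the plan says.** The protocol describes one group of 20 subjects, with enrolment of up to 24 to cover dropouts. Under Data Collection, Fluoroscopy, it says "Each subject will be asked to perform gait without the assistance of an offloading brace" and continues "Then, each subject will be fitted with a Breg, off-the-shelf OA brace and will perform normal gait while under fluoroscopic surveillance". The kinematic analysis text, under the JointVue ultrasound heading, says "Images will be captured at five instances during stance-phase of gait" and states the intended contrast: "A comparative analysis will be conducted for each subject while wearing the OA brace and with their non-braced test". That contrast is within subject.

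The SAP, Data Analysis, describes something else: "Statistical analysis of the data will be carried out to analyze the two cohorts". It checks normality with Shapiro-Wilk on the data as a whole, then adds "The data will also be tested for equality of variance", using Bartlett's and Levene's tests. These checks select one of three tests for every continuous variable: Student's t-test if the data are normal with equal variance, "Welch Anova test (when the data is normally distributed but has unequal variance", or "Wilcoxon Mann Whitney U-test (when the data is not normally distributed". All tests are at alpha 0.05. The SAP names no paired t-test, signed-rank test, repeated-measures model or analysis of differences.

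**The concern.** The protocol contains no second cohort. The two sets of readings come from the same knees, so the independence that the SAP's tests assume is false by design. Two further features follow from the same misreading:

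- Normality is checked on the data, whereas a paired t-test needs it for the within-subject differences.
- Equality of variance between conditions is tested, although a paired comparison does not assume it.

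Braced versus unbraced gait is the study's question, and each subject serves as their own control. An independent-groups test discards that advantage. If readings on the same knee are positively correlated, the test uses too large a standard error. The confidence interval is then too wide, and a real offloading effect may be declared non-significant. If the correlation were negative, false positives would exceed 5%.

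**Working it through.** **Inputs.** From the documents: alpha 0.05 (SAP) and n = 20, up to 24 (protocol). Not in the documents, so assumed: two-sided tests, normal data, equal SD in the two conditions, rho over a range, and a true difference of 0.5 SD for illustration. The documents give no power calculation, so alpha is the only figure to reproduce.

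**Formula.** For n pairs with common SD and correlation rho, the true variance of the mean difference is 2·SD²·(1 − rho)/n. The independent-groups test assumes 2·SD²/n. The true variance is therefore a fraction (1 − rho) of the assumed one. In large samples the actual level is 2·[1 − Φ(1.96/√(1 − rho))].

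- rho 0: 1.96/1 = 1.96, level 0.050. This reproduces the SAP's figure.
- rho 0.3: 1.96/√0.7 = 2.34, level 0.019.
- rho 0.5: 1.96/√0.5 = 2.77, level 0.006.
- rho −0.3: 1.96/√1.3 = 1.72, level 0.086.

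**Results at n = 20.** Levels and unpaired power come from 200,000 simulated trials per rho for the t-test and 20,000 for Mann-Whitney. Paired power is exact, from the non-central t distribution.

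| rho | Level, unpaired t | Level, Mann-Whitney | Power at 0.5 SD, unpaired t | Power at 0.5 SD, paired t | Difference detectable with 80% power (SD), unpaired / paired |
|---|---|---|---|---|---|
| 0 | 5.0% | 4.9% | 34% | 32% | 0.91 / 0.93 |
| 0.1 | 3.9% | 4.2% | 33% | 35% | 0.90 / 0.89 |
| 0.3 | 2.1% | 2.2% | 31% | 43% | 0.87 / 0.78 |
| 0.5 | 0.8% | 0.8% | 28% | 56% | 0.84 / 0.66 |
| 0.7 | 0.1% | 0.2% | 25% | 78% | 0.80 / 0.51 |

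Welch's test agrees with the unpaired t to within 0.002. The paired t-test holds its level at 4.9% to 5.1% throughout. At n = 24 and rho 0.5, power is 36% unpaired against 65% paired.

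**Whole selection sequence.** Simulating the SAP's full path (Shapiro-Wilk, then Bartlett and Levene, then the chosen test) at n = 20 gives a level of 0.051 at rho 0, 0.008 at rho 0.5 and 0.0001 at rho 0.8. The preliminary tests do not repair the problem.

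**Interval width, n = 20, rho 0.5, SD 1.** The unpaired 95% half-width is 2.024·√(2/20) = 0.640. The paired half-width is 2.093·√(2·0.5/20) = 0.468. The unpaired interval is 0.640/0.468 = 1.37 times as wide.

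**The case against.** Student's t-test is a name that also covers the paired form, and the protocol plainly intends a within-subject comparison. On that view this is a wording slip. The objection stands only in part. The protocol passage names no test. In the SAP the t-test depends on equal variance, which a paired t-test does not require, and the other two branches (Welch ANOVA and Mann-Whitney U) have no paired reading. Even a reader who assumes a paired t-test is sent to an independent-groups test whenever the data look non-normal or the variances unequal.

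The second objection is about severity, and most of it is fair:

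- For positive rho the error is conservative and creates no false positives.
- The documents state no power target, SD or effect size, so the loss breaches no promised figure.
- For a large effect the verdict would seldom change. At n = 20 and rho 0.5, power is 76% against 92% at 0.8 SD, and 94% against 99% at 1.0 SD.
- Very close to zero correlation the unpaired test is marginally more powerful, because it has 38 rather than 19 degrees of freedom. The crossover is near rho 0.04.

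These points limit the size of the harm. They do not make the planned analysis valid, and the intervals remain too wide for any appreciable positive rho.

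**Conclusion.** The concern holds. As written, the SAP applies independent-group methods to paired measurements of the study's central contrast, and the 0.05 level is not the actual level unless rho is zero. That last statement is exact for the t-test with normal data and equal variances, and approximate for Mann-Whitney and for the selection sequence.

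The size depends on rho, which the documents do not give. The loss is negligible near zero. At rho 0.5 the level falls to about 0.8% and power for a 0.5 SD difference is halved. At rho 0.7 power is 25% against 78%. A negative rho of −0.3 would instead raise the level to about 8.5%. Because this is the main comparison and the sample is small, it should be corrected before the data are analysed.

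**What to change.** In the SAP, replace the cohort wording with two conditions measured in the same subjects, and define the analysis variable as the within-subject difference, braced minus unbraced. State in advance whether the primary analysis uses the subject's mean over the five stance instants or a particular instant. If all five are tested separately, give a multiplicity rule.

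Report the mean difference with its 95% confidence interval and a paired t-test. If a normality check is kept, apply Shapiro-Wilk to the differences and use the Wilcoxon signed-rank test when p < 0.05. Delete the Bartlett and Levene tests, Welch ANOVA and Mann-Whitney U for this contrast.

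A mixed model over the five instants is an alternative only if it includes a random subject-by-condition term as well as the random subject effect. In 20,000 simulated null trials (20 subjects, five instants), a random intercept alone gave a level of 4.8% when the subject-by-condition variance was zero. The level rose to 10%, 17%, 24% and 33% when that variance was 0.1, 0.25, 0.5 and 1.0 times the residual variance. The paired t-test on subject means stayed at 4.7% to 5.3%.

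The cost is SAP wording only. The same data are used, and standard software provides these tests.

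### The SAP picks each test through normality and equal-variance checks built for two separate groups, although the protocol compares each subject with and without the brace

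*SAP*

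**What the plan says.** The SAP's Data Analysis section describes the data as two cohorts and sets up a sequence of checks. First, "The data will be first checked for normality using the Shapiro-Wilk test". The consequence is stated: "Only when the data is found to be normally distributed will parametric tests be used; otherwise, non-parametric tests will be used". Then "The data will also be tested for equality of variance using the Barlett's test and Levene's test". The choice of test rests on both checks; the sentence opens "The final selection criterion for the type of test to conduct will be based on the check for normality" and goes on to add equal variance. The rule is general: "for all the continuous variables, the following tests will be used". The list that follows has three entries: Student's t for normal data with equal variance, Welch ANOVA for normal data with unequal variance, and Mann-Whitney for non-normal data. No paired test appears.

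The protocol describes a different structure. Under Data Collection, Fluoroscopy, each subject walks first without a brace and then with one. The section on the JointVue ultrasound lists five instants of stance and says "A comparative analysis will be conducted for each subject while wearing the OA brace and with their non-braced test". The opening page gives 20 subjects, with enrolment raised to 24 for dropouts.

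The SAP leaves four things open: which quantity is checked, whether each instant is tested separately, the significance level of the checks, and what happens when Bartlett and Levene disagree.

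**The concern.** With one group measured twice, the analysis rests on the braced-minus-unbraced difference for each subject. The normality assumption of a paired t-test concerns those differences, and the spread of the two conditions need not be equal. Checks of each condition, and of equal variance between them, therefore answer a question that the design does not ask, and all three tests they lead to treat the two sets of measurements as independent.

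At stake are consistency and power. If the checks are run at each instant, one instant may be judged on means and the next on ranks, although both describe the same outcome in the same subjects. The protocol asks how much separation the brace produces, so the results across stance should be comparable. The larger cost is that the benefit of using each subject as his or her own control is lost whichever route is taken.

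**Working it through.** The SAP gives no operating characteristic for this procedure, and the documents state no effect size, SD or power, so there is no planned figure to reproduce.

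**Inputs from the documents.** 20 subjects (24 enrolled), two conditions per subject, five instants, alpha 0.05.

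**Assumptions not in the documents.** Checks at 0.05 on each condition at each instant; two-sided tests; Mann-Whitney if either Shapiro-Wilk check rejects, Welch if Bartlett or Levene rejects, otherwise Student; the correlations, distribution shapes and effect sizes shown below.

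**1. False alarms with truly normal data.** Two independent Shapiro-Wilk checks at one instant: 1 − 0.95² = 9.75% sent to Mann-Whitney (8–12% in simulation). Ten independent checks over five instants: 1 − 0.95¹⁰ = 40.1% chance of at least one switch.

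**2. Mixed tests across the five instants, normal data, n = 20.** Student and Welch both compare means, so only a switch to Mann-Whitney changes the hypothesis. A mix of mean-based and rank-based tests occurs in about 36–41% of simulated trials with correlation 0.5 between instants and 0.5 or 0.7 between conditions, and in 34–44% when both correlations range from 0 to 0.8. With n = 24 and correlations of 0.5 it is 41%, so the extra enrolment does not remove it.

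**3. Which quantity is checked.** Take a skewed subject effect (log-normal, sigma 0.5) shared by both conditions, plus normal noise, so that the differences are exactly normal. Shapiro-Wilk on the conditions rejects normality in 51% of data sets; on the differences it rejects in 5%.

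**4. What the checks alone do to the decision.** Compare the routed decision with that of an unpaired t-test used every time, at an assumed 0.62 SD shift and correlation 0.5 or 0.7:
- Normal data: the decisions differ in about 1–2% of comparisons, and power is about the same.
- Log-normal data, sigma 0.4: they differ in about 13–15%, and routed power is higher (61–64% against 51–52%).
- Type I error, normal data, correlation 0.5: 1.0% with and 1.0% without the checks.

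**5. What the unpaired tests do.** For a paired t-test, the standardised effect on the differences is d/√(2(1−ρ)) and the noncentrality is that value times √n.
- ρ = 0.5: 0.62/√1.0 = 0.62; 0.62 × √20 = 2.77; power 75%.
- ρ = 0.7: 0.62/√0.6 = 0.80; 0.80 × √20 = 3.58; power 92%.

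The SAP's procedure on the same normal data has simulated power of 48% and 47%, which is 27 and 45 percentage points lower. Its type I error is 0.9% and 0.15%, against about 5% for the paired test.

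**The case against.** The strongest defence is that the procedure is written down in advance and does little harm of its own. Much of this stands.

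- **Not fixed in advance.** A reader might infer that the analyst is free to choose. The documents do not support that: the rule is an algorithm. The discretion visible in it is the missing tie-break between Bartlett and Levene, which disagree in 0.4–4% of simulated normal comparisons.
- **Routing by chance.** A reader might infer that the checks mostly switch at random. Per comparison, about 90% of normal data are not sent to Mann-Whitney; the 40% arises by accumulating ten checks. With skewed data the switch responds to a real feature.
- **Significance driven by the checks.** Running both a t-test and Mann-Whitney on every comparison gives different decisions in roughly 8–11% (normal) or 16–21% (skewed). That is not the effect of the procedure, which applies one test per comparison; step 4 gives the relevant figures.
- **No estimate when the rank test is chosen.** The SAP names no estimate or interval for any of the three tests, and choosing Mann-Whitney does not prevent mean differences from being reported. That is a general omission, not a result of the checks.
- **Stated error of quantity.** The SAP never says that each condition is checked, or that this is done at each instant. Both are inferred from the two-cohort framing, the equal-variance tests, the scope over all continuous variables and the protocol's five instants.

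What remains is the mismatch with the design. Equal-variance checks and a list of two-sample tests have no place in a comparison within subjects, and no reading of the SAP leads to a paired test.

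**Conclusion.** The point holds in a limited form. The test-selection rule is framed for two separate groups and does not fit the protocol's paired comparison. On the natural reading it would also mix mean-based and rank-based tests across instants in about 36–41% of trials with identically normal data. The checks themselves are a minor fault: about 1–2% of decisions with normal data, about 13–15% with the assumed skew (where they raise power over a fixed unpaired t-test), and little added type I error.

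The substantial cost, power of about 47–48% against 75–92%, comes from being routed into unpaired tests. It should be counted once, together with the SAP's neglect of pairing. Its size depends on the assumed 0.62 SD effect and correlation of 0.5–0.7. With no within-subject correlation the gap disappears: at an assumed 0.5 SD shift, power is 34% unpaired and 32% paired. The mismatch with the design needs none of these assumptions.

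**What to change.** Amend the Data Analysis section of the SAP before analysis:

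- Specify a paired t-test on the braced-minus-unbraced differences, with the mean difference and 95% CI, at every instant.
- Report the Wilcoxon signed-rank test as a sensitivity analysis whatever the normality result.
- Delete the Bartlett and Levene checks.
- Keep Shapiro-Wilk on the differences as description only, with no role in choosing the test.

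This is a change of wording, with no extra data or subjects, and the same edit deals with the missing pairing. The price is some loss of power if the differences are strongly skewed, which the signed-rank result would show. Type I error is not a reason to keep the checks: in simulation a fixed paired t-test held 4.4–5.1% under normal and skewed data (log-normal, sigma 0.6), against 4.7–5.2% for a paired version with pre-testing.

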**In vivo Three-Dimensional Determination of
OA Brace Effectiveness**

[name]
 University of Tennessee
 [name]
 [name]
 [name]
 [contact]
 [contact]
 Email: [contact]

In vivo knee kinematics will be assessed for 20 subjects that have been clinically diagnosed with substantial unicompartmental osteoarthritis (OA) by one of the surgeons of Colorado Joint Replacement; this is the location from which participants will be recruited.

Enrollment will be increased to 24 subjects to account for any dropouts. Medial joint space narrowing will be clinically assessed in all patients on standing anteroposterior radiographs. The objective of this study will be to analyze subjects with symptomatic unicompartmental osteoarthritis under in vivo dynamic, weight-bearing conditions using video fluoroscopy to determine if present-day OA knee braces provide separation of the femoral condyle from the tibial plateau, thus avoiding excessive loads on the degenerative compartment.

The study will be submitted to Western IRB (WIRB); the University of Tennessee's IRB and Centura Health/Catholic Health Initiatives (for Colorado Joint Replacement/Porter Adventist Hospital) have waived oversight to WIRB. The required Reliance Agreements will be included with this submission to WIRB.

We will use the following inclusion criteria to recruit participants for this study:

1. Must be a patient of Colorado Joint Replacement.
2. Must be diagnosed with marked unicompartmental degenerative joint space narrowing.
3. Bilateral subjects may not be included in the subject population.

Exclusion criteria:

1. Pregnant, potentially pregnant or lactating females. To satisfy radiation protocol, each female subject will be asked if she is pregnant, or possibly could be pregnant. A pregnant person will not be allowed to participate in the study.
2. Subjects who are unable to perform normal walking.
3. Subjects who are unwilling to sign Informed Consent/ HIPAA documents.
4. Does not speak English.

Investigators

[name], Ph. D. (PI)
 [name] (Co-PI)
 [name] (Sub-I)
 [name], Ph. D. (Sub-I)
 [name] (Sub-I)
 [name] (Sub-I)

Study locations

Subject Recruitment will take place at Colorado Joint Replacement:
Colorado Joint Replacement
[name]
[name]
[contact]

Fluoroscopic exams, ultrasound exams and CT exams will be performed on all 20 (or possibly 24) subjects at: Porter Adventist Hospital

[name]

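### The SAP plans p-values from independent-sample tests but no group estimate or confidence interval for the within-subject change in medial separation

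*SAP*

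**What the plan says.** The protocol's opening section gives the objective as "to determine if present-day OA knee braces provide separation of the femoral condyle from the tibial plateau". Its section on JointVue three-dimensional ultrasound, where registration and comparison are described, says the bone models will be "overlaid onto the fluoroscopic images to determine amount of medial OA offloading". Each subject is compared braced and unbraced at five stance-phase instances, and "the amount of medial condylar separation will be assessed for each subject". The section on private health information confirms that separation with and without the brace is the subject-level measurement needed.

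The SAP's Data Analysis section describes extracting the kinematics by 3D-to-2D registration. It then describes the comparison as one between two cohorts, with Shapiro-Wilk, Bartlett and Levene checks leading to Student's t-test, Welch ANOVA or "Wilcoxon Mann Whitney U-test (when the data is not normally distributed". It closes with "All statistical tests will be carried out at 95% confidence level", explained in the same sentence as alpha 0.05. That is a test level, not a planned interval.

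On size, the protocol says "In vivo knee kinematics will be assessed for 20 subjects" and "Enrollment will be increased to 24 subjects to account for any dropouts". Neither document gives an SD, a power, a detectable effect, a within-subject correlation, a measurement error or a smallest separation of interest.

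**The concern.** The protocol's aim is to estimate an amount, while the SAP's statistical output is a p-value. The two do not meet: nothing in the SAP turns the per-subject measurements into a group change with a statement of its precision. On the rank-test route the named result has no size in mm at all.

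The objective can be answered no as well as yes, so a null result would need interpreting. Without an interval, a reader cannot see which amounts of separation remain compatible with the data. A significant result has the matching weakness, because it does not show how large the opening is. The listed tests also treat the two conditions as separate groups, although each subject supplies both readings, so any interval the software printed beside them would not be the right one for the change.

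**Working it through.** **Sample size.** The 20 cannot be reproduced, because no effect size, SD or power is given. The step from 20 to 24 corresponds to a dropout of 4/24 = 16.7%, but no rate is stated.

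**Inputs.** n = 20 subjects, each measured in both conditions (protocol); alpha 0.05 (SAP). Assumptions: two-sided testing, since sidedness is not stated, and equal SD in both conditions. Results are in SD units only.

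**Two units.** SD is the between-subject SD within a condition. SDd is the SD of the within-subject differences. With within-subject correlation ρ, SDd = SD × √(2(1 − ρ)), so the two coincide only at ρ = 0.5.

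**95% CI half-width, n = 20.**
- Paired: t(0.975, 19)/√20 = 2.093/4.472 = 0.47 SDd.
- Unpaired, as listed: t(0.975, 38) × √(2/20) = 2.024 × 0.316 = 0.64 SD.

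Converting the paired figure to SD over an assumed range of ρ:

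| ρ | Paired half-width (SD) | Unpaired half-width (SD) |
|---|---|---|
| 0 | 0.66 | 0.64 |
| 0.3 | 0.55 | 0.64 |
| 0.5 | 0.47 | 0.64 |
| 0.7 | 0.36 | 0.64 |
| 0.9 | 0.21 | 0.64 |

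The paired interval is the narrower one once 2(1 − ρ) falls below (0.640/0.468)² = 1.87, that is, for ρ above about 0.06.

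**Power, noncentral t, n = 20.**
- Paired: noncentrality δ√20, 19 df. At δ = 0.5 SDd it is 2.24 and power is 56%. For 80% power δ = 0.66 SDd.
- Unpaired, with the two sets of readings treated as independent: noncentrality δ√(20/2), 38 df. At δ = 0.5 SD it is 1.58 and power is 34%. For 80% power δ = 0.91 SD.

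A true change of that half-SD size would therefore be non-significant about 100 − 56 = 44% of the time in the paired analysis and 100 − 34 = 66% in the unpaired one. Because the units differ, the two percentages describe the same true change only at ρ = 0.5. The unpaired power is also nominal: with correlated readings the real rejection rate of that test would differ.

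**If all 24 are analysed.** The paired half-width is 0.42 SDd and the 80% figure is 0.60 SDd. The unpaired figures are 0.58 and 0.83 SD. The picture does not change.

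**The case against.** The strongest reply is that the amounts will exist. The protocol plans them for every subject in both conditions, the SAP extracts the kinematics behind them, and the software will probably print means and intervals. This stands in part. A reader might infer that the plan yields nothing but tests, or that no per-subject result is planned. The protocol contradicts that. What remains is narrower: the SAP commits to no group summary or interval, and output that software may print is not a prespecified result.

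A reader might also infer that the sponsor will report a non-significant test as showing that the brace does not work. Neither document says so. The SAP is silent on interpretation, which is an omission and not a wrong rule.

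A third tempting inference is that the study is likely to miss an effect of about one SD, because a paired result just short of significance has an interval reaching 2 × 0.468 = 0.94 SDd. That confuses the upper limit of a borderline interval with the chance of missing a true effect that large. Paired power is about 98% at 0.94 SDd and 99% at 1.0 SDd. Even the unpaired t-test has nominal power of 87% at 1.0 SD. The real uncertainty lies with moderate effects, around half an SD.

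Finally, the use of unpaired tests can be called a separate defect. It is, but moving to paired tests alone would still leave a plan that promises only p-values.

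**Conclusion.** The point holds in this limited form. Per-subject amounts are planned, but the only statistical output the SAP commits to is a p-value from one of three independent-sample tests, with no group estimate of the within-subject change and no confidence interval. At n = 20, 80% power needs 0.66 SDd with a paired t-test and 0.91 SD with the listed unpaired one. At half an SD, power is 56% and 34% respectively. A non-significant result alone therefore cannot distinguish absence of separation from failure to show it.

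These figures rest on two-sided 0.05, t-based calculations and, for the unpaired test, independent readings. They are in SD units, and no statement in mm is possible from the documents. The SAP should be changed. The defect lies in the planned analysis and reporting, and it does not affect the data to be collected.

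**What to change.** In the SAP's Data Analysis section:

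- Make the main result the mean within-subject change in medial separation (braced minus unbraced, in mm) with its paired 95% CI.
- Fix in advance where it is measured: one named stance instance, or a prespecified average of the protocol's five. Otherwise there would be five intervals and no rule for choosing among them.
- If the differences are clearly non-normal, give the paired Hodges-Lehmann estimate with its CI.
- State that this replaces the independent-sample tests for this comparison. That is a correction to a paired analysis as well as an addition to reporting.
- List or plot each subject's change.
- Report a non-significant result through its interval, not as evidence of no separation. If the sponsor wants to be able to conclude that there is no meaningful separation, it must name the smallest separation of interest beforehand and justify it against measurement error. The documents give no such value, and none is proposed here.

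A count of knees that opened should be left out unless a measurement-error threshold is set in advance. With symmetric noise and no brace effect, about half the knees would be expected to count as opened.

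The cost is a short paragraph and a little more output from data already planned, with no extra subjects or imaging. The downside is that some null results will read as inconclusive.
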